- Inability to provide informed consent.
- Being deemed unable to comply with the study protocol

Implementation phase

The study implementation phase will be conducted at 30 HIV clinics located in Lagos, Nigeria. Sites and participants for the proposed study will be recruited from the list of over 67 HIV clinics registered with the Lagos State Healthcare Board. The NIMR will recruit 960 patients from 30 HIV clinics from this list under the guidance of Lagos State AIDS Control Agency which funds comprehensive care for its HIV patient network in Lagos State. Note that this means recruitment of 32 participants at each of the HIV clinics. Eligibility criteria for study participants are outlined below.

Inclusion criteria

- Be an adult aged 18 years and older.
- Attends one of the 30 HIV clinics.
- Have a diagnosis of HTN with uncontrolled blood pressure, i.e. BP is 140-179/90-100 mm Hg.
- Ability to provide consent.

Exclusion criteria

- BP>180/110 mm Hg;
- history of chronic kidney disease, heart disease, diabetes
- or stroke, pregnancy
- Inability to provide informed consent.

Refusal to participate in the study.

Inclusion of vulnerable populations

Participants with cognitive impairment are not eligible to participate.

Sources of materials

These will include paper-and-pencil as well as web-based questionnaires, audiotaped sessions and semi-structured interviews and standard participant chart data. All data will be used specifically for research purposes. The data analyst, under the supervision of the study statistician ([name]) will work with the [name] from NIMR the Research Coordinating Center to send de-identified participant level files to NYU. NYU will give the data managers in NIMR a range of unique study identifiers to assign to participants. The analyst will keep a table of these identifiers once they have been assigned for the duration of the study. Using this method, we will ensure that confidentiality of participants is maintained but that participants who are observed more than once will have the same study ID in each extract. A pre-defined set of measures will be exported from the data warehouses into a de-identified Excel spreadsheet or delimited text file.

Potential risks and protection against risks

Though we expect the level of risk due to this intervention to be minimal, potential risks to the participant may include the following:

Violation of participant privacy and confidentiality

Loss of confidentiality is the greatest potential risk to study subjects. We will obtain written consent from all study participants who participate in surveys and interviews; however, no identifying information will be included on the transcripts of interviews or surveys. As part of the process involved in obtaining written informed consent, all participants will be reminded that their responses are confidential and that they may refuse to participate in the project or withdraw at any time without explanation, and further, that such an action will in no way affect their treatment or future interactions with their providers. Also, if a participant is

uncomfortable during a research encounter, they may stop at any time. All survey data entered into the research database will be protected by confidential entry codes. Names will be replaced with identification numbers. All health record data will be de-identified prior to transfer from the data warehouses to the central repository managed by NYU. Locked file cabinets will be used to store materials with identifying information (e.g., participant consent forms). Only members of the research team will have access to participant's personal information file. Study data will be transmitted to [name] and the data analyst for data processing using only secure methods (e.g., encrypted email). All electronic audiotaped data will be saved on a secure server housed by NYULH and backed up daily or weekly depending upon the receipt of data. Participant health information will be confined to a secure server that is not connected to the Internet. All computers are password protected and on a private LAN network. No file and database servers are accessible to the public through the Internet. Prior to inclusion in any data set (internal and external), data will be stripped of all identifying information. Finally, the web-based surveys will be accessed via a HIPAA compliant application. The data collected for this study will be used strictly for the purposes stated in this grant application and will only be available to relevant research staff at the Nigerian Institute of Medical Research, Washington University in St. Louis and NYU. IRB approval will be sought prior to any data collection involving human subjects. Finally, all identifiable participant health information will be obtained and managed in accordance with the HIPAA Privacy Rule, 45 CFR Parts 160 and 164.

Anxiety

There is a potential risk that participants may feel uncomfortable or anxious during the audiotaped sessions and/or semi-structured interviews. To mitigate this potential challenge, the study staff member who conducts the semi-structured interview will be trained to act professionally and address all participants' concerns. Participants will also be reminded that the tapes are only for research purposes and will not influence their relationship with the provider. Moreover, participants will be reassured that the tapes will be saved in a secure and confidential database that only the study staff will have access to, and that have the right to ask that the tapes be deleted if they feel sensitive information was discussed during the session that they do not want the research team to hear.

Adequacy of protection against risks

Recruitment and informed consent

Study staff will be responsible for recruitment of subjects and data collection. Researchers are required to be trained in Human Subjects and HIPAA policies and procedures and the handling of data to ensure the confidentiality in order to obtain Institutional Review Board (IRB) approval from NYULH. Clinic key personnel and staff will be told about the study at a group meeting. Participation is voluntary and written consent is obtained from participants prior to conducting baseline procedures, and after a detailed explanation of the study is provided by the research staff. Survey data will be entered into a password protected laptop computer or tablet using a web-based portal housed on a secure NYULH server. Once potentially eligible participants are referred to the study staff, the study coordinator will provide a more in-depth description of the study to the participant in clear, easy-to-understand language. If the participant remains interested in participating, the study coordinator will provide a copy of the consent form for the participant to read; if the participant asks for help or indicates that they have a problem reading the consent form, the study coordinator will read the consent form to the participant. If the participant agrees to participate, s/he will sign the consent form or provide a thumbprint in lieu of a signature for participants who cannot read or write.

Potential Benefit of Proposed Research to Human Subjects and Others

The intervention is expected to benefit the participants by improving their blood pressure control, reducing their cardiovascular risk profile, and increasing their role as active participants in the management of their HTN. The intervention is expected to benefit the participants. The ultimate aim is to develop a facilitation strategy that can be delivered nationally at little expense; thus, the benefit to others will occur when the intervention becomes a routine part of activities at the HIV clinics. Overall, the benefits of understanding effective methods for helping vulnerable populations, i.e. people living with HIV (PLWH), reduce their cardiovascular risk far outweigh the remote possibility of a breach of confidentiality. The study may also have relevance to other HIV clinics by

testing new strategies to enhance implementation of evidence-based interventions for improving hypertension control in high-risk populations.

SECTION 11 : Data and Safety Monitoring Plan

In compliance with NIH requirements, we will establish a data and safety monitoring plan (DSMP). The purpose of the DSMP is to ensure the safety of participants and the validity and integrity of the data. Personnel involved in the monitoring activities will include:

- The Principal Investigators on this application.
- Designated medical monitor (a physician in our program who will provide consultation on medical risks and who will review adverse events).
- Internal Committee (The PIs, and the Co-Investigators on the present proposal).
- Institutional Review Board.

The data and safety-monitoring plan will comprise the following elements:

- Reporting of adverse events to the IRB and to NIH trials: Adverse events will be reported to the IRBs. Summaries of adverse events reports will be made to NIH in the yearly progress report or at the end of year 5, in the final report, unless the nature of a particular event is such that it bears reporting to NIH immediately.
- A detailed plan to deal with serious events that may arise, such as blood pressures that indicate a hypertensive emergency that occur during the baseline and follow-up periods (these are the only times that any of our personnel will take such measurements). The plan will include a step-by-step algorithm to deal with such events.
- The PIs and the co-Investigators will meet yearly to review adverse events reports, patient complaints if any, and dropout rates. Data will be provided at those meetings by the investigators on key variables that may indicate harm, including changes in blood pressure and self-reported adherence to medication regimen for people living with HIV (PLWH). The biostatistician will evaluate confidentiality and integrity of the database, and the procedures for recording and storing confidential files. The investigators will also review the elements of the plan to deal with emergencies.
- Protect the confidentiality of the trial data and the results of monitoring.

SECTION 12: Study Records Retention

This study will comply with the NYULH policy on research record retention. Specifically, all research data accessed by NYUSM study personnel will be maintained on MCIT DataCore-approved EDC systems, and accessed only via MCIT-approved computers via authorized and approved study personnel.

SECTION 13: Publication and Data Sharing Policy

Our commitment to translating efficacious interventions into routine “real world settings” and to supporting the potential for sustainability has informed the selection of partners, the design of the practice facilitation intervention, and the governance structure for the project, as well as our strategies for disseminating insights from the implementation (process) and outcomes evaluation. This plan will be executed by a Dissemination Committee that we will set up for the purpose of this study. Through regular meetings with the Steering Committee throughout the grant period, we will engage key stakeholders at the participating HIV clinics, Lagos State AIDS Control Agency (LSACA), and the Lagos State Primary Health Care Board to assist with refining our approach to enhance relevance and usability, disseminating findings at regular intervals and providing expertise on the external context in which the study approach is being implemented. Upon the successful completion of the project, the study PIs in collaboration with key agencies such as the Nigerian Ministry of Health will work together to develop effective measures for rolling out the intervention to control sites

throughout Lagos State. This roll-out effort will include periodic refresher trainings for HIV clinic nurses at the control sites and collaborations with regional/ state primary healthcare agencies to establish effective protocols for integrating TASSH within their respective clinics.

The dissemination of evidence-based health interventions in low income countries has been hampered by a lack of “infrastructure for marketing and distribution.” Key to all forms and stages of dissemination will be NYU Langone Health’s (NYULH) robust communications and marketing department, which is designed to disseminate best practices in public health and care processes as well as the development of external publications and press releases as program findings emerge. In addition, the National Institute of Medical Research (NIMR’s) communication office will handle the dissemination to key stakeholders. To facilitate dissemination more broadly, we will develop a dissemination toolkit that provides guidance on how to support implementation of practice facilitation in the HIV clinics. Our dissemination toolkit will have four main components: 1) presentations at scientific conferences; 2) publications in high impact relevant peer-reviewed journals; 3) establishment and maintenance of a website for dissemination of research findings; and 4) presentation of study findings at stakeholders’ forums.

In accordance with NIH requirements, we will register the trial in clinicaltrials.gov, as mandated under Public Law 110-85, no later than 21 days after the first subject is enrolled. We will also report the summary of all results no later than one year after the completion date. The Clinical Research Support Unit and Human Research Regulatory Affairs offices support investigators at NYULH in initiating, conducting, and managing studies by providing guidance in several crucial areas, including post-award management and compliance with grant policy requirements (e.g., registration and maintenance of ClinicalTrials.gov accounts). We will ensure that our informed consent documents clearly state that information related to the trial will be posted on ClinicalTrials.gov. All participants will need to initial this statement to signify that they understand and agree to this requirement. The team will also disseminate research findings through presentations at international meetings. We will publish findings in peer-reviewed journals, and other venues.

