Assessment of Potential Risks and Benefits: Potential risks and benefits will be assessed at each study visit (Baseline, 6, 12, 24 months). Detailed assessment of risks and benefits is listed under Study Assessment and Procedures.

SECTION 3: Study Objectives

Primary objective, endpoint, and justification

The primary objective is to compare in a cluster RCT of 30 HIV clinics, the effect of PF intervention versus a self-directed condition (receipt of information for implementation of TASSH but no facilitation) on systolic BP reduction among 960 HIV patients with HTN (BP>140/90 mmHg).

The primary outcome is change in systolic BP (SBP) from baseline to 12 months. Following existing TASSH protocol, the SBP reduction in patients will be assessed as mean change in systolic BP from baseline to 12 months. Blood pressure will be taken with valid automated BP device as follows:

At baseline, three BP readings will be taken by trained research coordinators using an automated BP monitor with participant seated comfortably for 5 minutes prior to the measurements. The average of three BP readings will be used as the measure for each visit. The same procedure will be followed at the 12-month study visit.

Justification: Uncontrolled BP is defined as average clinic systolic BP>140 mmHg or diastolic BP>90 mmHg following the guidelines set forth by WHO for CVD treatment and in accordance to the Nigerian healthcare policy. Adopting these guidelines currently instituted within the Nigerian healthcare system will ensure sustainability of the proposed study's procedures.

Secondary objective, endpoint, and justification

The secondary objectives are to:

- Compare in a cluster RCT of 30 HIV clinics, effect of the PF intervention versus self-directed condition (receipt of information for implementation of TASSH but no facilitation) on TASSH adoption and sustainability.
- Determine the mediators of adoption and sustainability of TASSH across the 30 HIV clinics at 12 months and 24 months respectively.

Secondary outcomes are:

- Rate of adoption and sustainability of TASSH across the PHCs at 12- and 24 months respectively.
- The mediators of TASSH across the HIV clinics at 12 and 24 months.

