The study implementation phase will be conducted at 30 HIV clinics located in Lagos, Nigeria. Sites and participants for the proposed study will be recruited from the list of over 67 HIV clinics registered with the Lagos State Healthcare Board. The NIMR will recruit 960 patients from 30 HIV clinics from this list under the guidance of Lagos State AIDS Control Agency, which funds comprehensive care for its HIV patient network in Lagos State. Note that this means recruitment of about 32 participants at each of the HIV clinics. Eligibility criteria for study participants are outlined below.

Inclusion criteria

- Be an adult aged 18 years and older.
- Attends one of the 30 HIV clinics.
- Have a diagnosis of HTN with uncontrolled blood pressure, i.e. BP is 140-179/90-100 mm Hg.
- Ability to provide consent.

Exclusion criteria

- BP>180/110 mm Hg;
- history of chronic kidney disease, heart disease, diabetes
- Stroke,
- pregnancy
- Inability to provide informed consent.
- Refusal to participate in the study.

Screen Failures

Screen failures will be referred to the PHCs for further management as is done in routine practice.

Strategies for Recruitment and Retention

The research staff will conduct the screening, consent, enrollment, and all study assessments. The study will recruit 30 HIV clinics from the network of 67 HIV clinics, who are part of the 100 primary care practices managed by the Lagos State Healthcare Board (LSPHB). All 67 HIV clinics are affiliated with the Lagos State AIDS Control Agency, which utilizes LSPHB to provide comprehensive primary care services to PLWH. Eligible HIV clinics will be selected from areas geographically distinct from one another. Once a clinic agrees to participate, their director will be asked to sign an MOU and identify 2 HIV nurses to be trained. Eligible patients will be identified from the HIV clinics during routine visits. Each clinic will recruit 32 patients using these inclusion criteria: 1) patient receiving care at the clinic; 2) adults 40 years and older; 3) BP 140-179/90-100 mm Hg; and 4) can provide informed consent. Exclusion criteria: 1) BP>180/110 mm Hg; history of chronic kidney disease, heart disease, diabetes or stroke, pregnancy; 2) inability to provide consent; and 3) refusal to participate.

SECTION 4: Study Intervention

Description of Study Intervention and its Administration

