All 30 HIV clinics enrolled will begin the study as part of the pre-implementation phase for 12 months, after which they will be randomly assigned to either the PF intervention (N=15) or the self-directed condition (N=15). Once randomized, the PHCs will participate in the 12- month implementation phase (intervention period) followed by a 12-month post- implementation period to assess its sustainability.

Randomization will occur in 5 cohorts of 6 PHCs every 6 months for 30 months and will be stratified by cohort to ensure balance over time. Upon completion of recruitment for each cohort, the clinics will be randomized in a 1:1 ratio to either the PF intervention or self-directed condition (i.e. receipt of information on TASSH implementation without PF). The sequence of randomization will be generated by [name], and kept in secure electronic format inaccessible to study sites, in accordance with CONSORT guidelines. Sites will be

informed of their randomization group by telephone. Because of the nature of the intervention, it is impossible to blind the patients, lay health advisors, and the study coordinators to the group assignment. The data analysts will remain blinded to treatment assignment until the completion of the implementation phase, defined as the period from baseline to 12-month follow-up(primary endpoint). During the post-implementation phase, the practice facilitators will leave the intervention sites and will have minor direct influence on the TASSH adoption. As the intervention concludes, data analysts will be unblinded following the primary endpoint. Preliminary database containing baseline and 12-month follow-up data will be locked upon unblinding for analysis.

Study intervention compliance (Group A).

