Follow-up Study Visits (6, 12, 18, and 24 months): The research coordinator (RC) will meet with each patient to collect follow up data on primary outcome measure (BP measurements identical to that described for the baseline visit) and secondary outcomes. Study measures for both groups are similar and will be conducted in the same manner by the RC. Patients in the HIV clinics randomized to the Self-Directed Group will attend follow up study visits as scheduled while those in the clinics randomized to the PF Intervention will meet with their nurses every three months [for lifestyle counseling and treatment] in addition to the scheduled study visits.

On-time Follow-up Study Visits (6, 12, 18, and 24 months): On-time visit occurs within a +/- 3-months window of the expected follow-up date. For the 6-month follow-up visit, an on-time visit occurs between 3 and 9 months after baseline visit. For the 12-month visit, an on-time visit occurs between 9 and 15 months. For the 18-month visit, an on-time visit occurs between 15 and 21 months.

Baseline visits: The RC will confirm eligibility status and obtain informed consent from each patient. At baseline, we will measure the organizational and individual-level factors shown to affect implementation of evidence-based practices, including leadership, organizational capacity to change, individual attitudes toward evidence-based practices, and the degree of buy-in among practice facilitators.

SECTION 6: Study Measures

Primary Outcome: Change in systolic BP from baseline to 12 months. The SBP reduction in patients will be assessed as mean change in systolic BP from baseline to 12 months.

Secondary Outcomes are:

Adoption [proportion of patients who were correctly diagnosed with HTN, received lifestyle counseling and antihypertensive treatment]; and *sustainability* [maintenance of TASSH uptake at the HIV clinics at 24 months].

The mediators of TASSH across the HIV clinics at 12 and 24 months.

Assessment of Outcome Measures:

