- Any other unanticipated problem will be reported to the IRB within 2 weeks of the investigator becoming aware of the problem.
- All unanticipated problems should be reported to appropriate institutional officials (as required by an institution's written reporting procedures), the supporting agency head (or designee), and OHRP within one month of the IRB's receipt of the report of the problem from the investigator.

Data collection, handling, record keeping

A real-time electronic data collection system will be established in accordance with stringent data management protocols of Nigerian Institute of Medical Research (NIMR). Data will be entered into a web-based electronic database capture system called Research Electronic Data Capture (REDCap). Electronic data collection forms will be developed using the REDcap platform and deployed on tablets for the data collection. Data collection will be done by HIV nurses and hosted on a server at NMIR. These forms have in-built data validation and consistency checks. Dedicated study data managers at NIMR will review study data on a weekly basis, generate queries on outliers and send written queries to the field for correction and updates.

Access to source documents, case reports forms, other data and information

The Principal Investigators will be responsible for sharing and granting access to data generated from the study. Data will be shared among the investigators via an electronically secured method that encrypts data during transfer. The data will be reviewed by the PIs and, study data managers and study statistician on a monthly basis and issues raised will be communicated to the project coordinators to be addressed during the coordinator's periodic visits to the data collection sites in Nigeria. For essential documents, a paper form regulatory binder will be utilized. Paper records would be stored in a study-specific regulatory binder or file. The site Principal Investigator would approve all source documents before it is made accessible.

Statistical Considerations

Data analysis: primary outcome, associations to be studied, techniques to be used

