Identifying HIV clinics: The NIMR will be responsible for all recruitment activities. NIMR has deep connections with the Lagos State Healthcare Board and its network of over 67 HIV clinics in Lagos, Nigeria given its previous work with these organizations. Currently, there are over 67 clinics affiliated with NIMR; we will recruit 30 HIV clinics for this study. Two Research Coordinators (RC) will be hired by NIMR to conduct the screening, consent, enrollment, and all study assessments. [name] will supervise recruitment and retention activities of the research staff.

Recruitment of HIV Clinics: We will recruit HIV clinics that are affiliated with the Lagos State Primary Health Care Board, which is also affiliated with the Lagos State AIDS Control Agency (LSACA). [name] will meet with clinic leaders to provide study overview. All eligible HIV clinics must be a NIMR-affiliated clinic - there are 67 across Lagos. Eligible clinics will be selected from areas geographically distinct from one another with equal urban/rural mix. Once a clinic agrees to participate, their key leadership personnel will be asked to sign a MOU and identify 2 nurses to be trained to deliver TASSH.

Participant recruitment strategy: The RCs will work with nurses to develop a recruitment strategy specific to the clinic. Once the nurse has identified a participant who meets the inclusion criteria, the person is given a telephone number of the RC to call if they are interested in the study. During the call, the RC will give a brief explanation of the procedures, including the following: that participants will have a 50-50 chance of being in the Practice Facilitation Strategy or Self-Directed Condition (depending on which group their clinic is randomized to); that not every participant is accepted into the study (this will be decided during the screening visit). If the person desires to participate at this point, an in-person appointment for the consent/screening visit is then set for the participant with the RC and nurse.

Characteristics of the study population during the pre-implementation and Implementation phase

Pre-implementation phase

This phase will involve 70 participants, who are steering committee members, key stakeholder or user testers (Nurses, physicians, patient advocate, Directors HIV clinics). Eligibility criteria for study participants are outlined below.

Inclusion criteria

- Be an adult aged 18 years and older.
- Ability to provide consent.

Exclusion criteria

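### The 12-month systolic BP is taken by coordinators who, on the likeliest reading, cannot be blinded, with no device-captured record, and the data-collection roles of coordinators and HIV nurses conflict

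*Combined protocol and SAP*

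**What the plan says.** **The outcome and who measures it.** Section 3 states: "The primary outcome is change in systolic BP (SBP) from baseline to 12 months". The same section says "At baseline, three BP readings will be taken by trained research coordinators using an automated BP monitor", and that the 12-month visit follows the same procedure. Section 5 (Follow-up Study Visits) says "The research coordinator (RC) will meet with each patient to collect follow up data on primary outcome measure". Section 10 (Identifying HIV clinics) says "Two Research Coordinators (RC) will be hired by NIMR to conduct the screening, consent, enrollment, and all study assessments".

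**Blinding.** Section 4 (Randomization, Measures to minimize bias, and Blinding) gives the nature of the intervention as the reason that "it is impossible to blind the patients, lay health advisors, and the study coordinators to the group assignment". The only role it keeps blinded, up to the primary endpoint, is the data analyst.

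**Who collects data.** Section 6 (Data collection, handling, record keeping) says "Data collection will be done by HIV nurses and hosted on a server at NMIR". Strategies for Recruitment and Retention, in Section 3, says "The research staff will conduct the screening, consent, enrollment, and all study assessments".

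**Safeguards.** BP is measured with an automated monitor after five minutes seated, and the three readings are averaged. Measures are carried out the same way in both groups. Baseline collection is complete before a clinic is randomized. REDCap has built-in checks, and data managers query outliers weekly.

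**The concern.** An automated device does not decide how long the patient really rested, whether a reading is repeated, or what is typed into the tablet. Those choices stay with the person doing the visit. If that person knows the clinic's arm, a small systematic difference can enter the 12-month readings. The Aim 2 model estimates the effect as the arm-by-time interaction. An error that is absent at baseline and differs between arms at follow-up therefore goes directly into the estimate. Blinding the analysts cannot remove it.

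The stated reason for not blinding also does not clearly reach the BP measurers. Facilitation is delivered to the nurses by the practice outreach facilitators, and BP is to be measured identically in both arms, so measuring it does not require knowing the allocation.

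The sentence giving data collection to the nurses adds a second uncertainty. In the practice facilitation (PF) arm these nurses are coached and receive performance feedback; in the other arm they get no facilitation. Who may write to the study BP fields should not be left to interpretation.

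**Working it through.** **Step 1: are the unblindable coordinators the people who measure BP?** Section 4 says *study coordinators*; Sections 3, 5 and 6 say *research coordinators* for BP. The documents never equate the titles. Section 10 (Recruitment and informed consent) says "the study coordinator will provide a copy of the consent form for the participant to read", and Section 5 and Section 10 (Identifying HIV clinics) give consent to the RC. The two titles share a task, so the same-staff reading is well supported though not proved. On any reading, no section names a blinded BP assessor.

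**Step 2: do the role statements agree?**

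| Place | Task | Assigned to |
|---|---|---|
| Section 3, Primary objective | BP at baseline | Research coordinators |
| Section 3, Recruitment and Retention | All study assessments | Research staff |
| Section 5, Follow-up Study Visits | Primary-outcome data | RC |
| Section 10, Identifying HIV clinics | All study assessments | Two RCs |
| Section 6, Data collection | Data collection, no limit stated | HIV nurses |

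The last row conflicts with the three above it. It does not mention BP.

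**Step 3: which readings are exposed?** Baseline is taken before allocation, so knowledge of the arm cannot affect it. The 6-month and later readings, including the 12-month endpoint, come after allocation.

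**Step 4: how much could a small error matter?** The documents give no alpha, power, SD, ICC or size of measurement error for this outcome, so there is no planned figure to reproduce. What follows is an illustration.

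- From the documents: 30 clinics, 15 per arm, 32 patients each (30 × 32 = 960; 15 × 32 = 480 per arm).
- Assumed: SD of change 15–20 mmHg, ICC 0.01–0.10, two-sided alpha 0.05, no true effect, full retention, and a 1 mmHg difference between arms in 12-month measurement error.
- Design effect DE = 1 + (32 − 1) × ICC.
- SE = SD × √(2 × DE / 480).
- False-positive rate: chance that a non-central t on 30 − 2 = 28 df, with non-centrality 1/SE, exceeds the two-sided 5% limits.

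Example: SD 15, ICC 0.01 gives DE = 1 + 31 × 0.01 = 1.31 and SE = 15 × √(2 × 1.31 / 480) = 1.11 mmHg.

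| SD | ICC | DE | SE (mmHg) | False-positive rate with 1 mmHg error |
|---|---|---|---|---|
| 15 | 0.01 | 1.31 | 1.11 | 14.1% |
| 15 | 0.05 | 2.55 | 1.55 | 9.6% |
| 15 | 0.10 | 4.10 | 1.96 | 7.8% |
| 20 | 0.01 | 1.31 | 1.48 | 10.0% |
| 20 | 0.05 | 2.55 | 2.06 | 7.6% |
| 20 | 0.10 | 4.10 | 2.61 | 6.6% |

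With no error the rate is 5%. The cluster t-test stands in for the planned mixed model.

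**The case against.** **The job titles are loose.** Section 4 also uses *coordinator* for the facilitators, and Section 6 mentions project coordinators, so the blinding sentence might not mean the BP measurers. That ambiguity stands. It is a reason to clarify, and it does not supply a blinded assessor.

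**The nurses have data of their own.** They keep attendance logs, complete the adoption questionnaire and record referrals electronically. The sentence in Section 6 may mean only that. A reader might infer that nurses measure or enter the outcome BP; the documents do not support this, because every passage that names the measurer of outcome BP names a coordinator. Section 11 likewise has study personnel measuring BP at baseline and follow-up. A reader might also infer that nurses work to an imposed BP target. Section 4 has the nurses themselves setting targets for their centres as part of TASSH implementation, and no target is set for the SBP outcome. What stands is an unrestricted sentence that conflicts with other sections.

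**Safeguards exist, and full masking is unlikely.** The standard procedure narrows the route to bias, and having the same two RCs in both arms means their general habits are largely shared. The RCs belong to the study team that meets every two weeks and work with clinic nurses. Patients are not blinded, and only PF patients have scheduled three-monthly nurse meetings. All of this stands. It limits what masking can achieve, but it does not affect objective capture of readings or clear entry rights, which work even if masking fails. Outlier queries would not detect a small systematic shift.

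**The size is assumed.** Any assumed bias inflates type I error. A 2 mmHg error in the same calculation gives about 12–41%, but the upper end combines the smallest SD and ICC with full retention. A reader might take such figures as evidence that the trial is biased. They are not: the documents give no basis for the size of any such error, or for assuming that one will occur.

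**Conclusion.** The concern holds in limited form. On the best-supported reading, the 12-month primary outcome is measured by staff the protocol says cannot be blinded, and nothing requires device-captured readings. Section 6 also assigns data collection in a way that conflicts with Sections 3, 5 and 10.

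The exposure is confined to discretion and manual entry at post-randomization readings. Its size is unknown. If a 1 mmHg difference between arms arose, the false-positive rate would be about 7–14% in place of 5%, under assumed SD 15–20 mmHg and ICC 0.01–0.10. This is a weakness at the primary endpoint that is worth correcting because correction is cheap; it does not undermine the design.

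**What to change.** 1. **Reconcile the roles.** Amend Section 6 (Data collection, handling, record keeping) so that nurses enter only TASSH logs, adoption questionnaires and referral data, and only RCs enter study BP. Set REDCap write permissions to match. State in Section 4 whether *study coordinators* are the RCs.
2. **Measure BP first.** Take it before any other assessment at the 12-month visit.
3. **Keep an objective record.** Record all three readings from the device memory, or from a time-stamped photograph of the display.
4. **Mask as far as practicable.** Do not tell the RCs who measure BP the clinic's allocation, keep them out of arm-specific discussions, and record whether they became aware of it.

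The cost is minor protocol, database and scheduling work, with no new staff. Masking will be incomplete because RCs may infer the allocation on site; items 1 to 3 do not depend on it.
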